### Geometric Mean Titers (GMTs)

GMTs measured by ELISA and PRNT will be calculated at Visits 1, 3, 4, 6, 7, FU 1 and FU 2 for each treatment group and for combined groups as indicated.

Descriptive statistics will be derived by visit including number of observations available at each visit (n) and GMT with 95% CI (derived by the antilogarithm of the 95% CI of the  $\log_{10}$  titer transformations). GMTs and upper and lower confidence limits will be displayed to one decimal place.

The ratio of the GMTs will be presented between Group 2 and the combined Group 1 / Group 3 at Visit 4 along with the 95% CI. Similarly, the ratio of the GMTs will be presented between

Group 3 at Visit 7 and Group 1 / Group 2 separately at Visit 4, and at the FU Visits (FU 1 and FU 2) the ratios of the GMTs will be presented between Group 3 and Group 1 / Group 2 separately. Lastly, the ratios of the GMTs at Visit 1, 3, 4, FU 1 and FU 2 will be presented between Group 1 and Group 2 / Group 3 separately.

A line chart will be presented showing the GMTs measured by ELISA and PRNT per treatment group for each visit for the PPS and the FAS.

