## 4 Trial Design

### 4.1 Experimental Design

Randomized, open-label Phase II trial to assess the safety and immunogenicity of MVA-BN® smallpox vaccine when increasing the number of injections compared to the standard regimen in immunocompromised subjects with HIV infection

In total, 90 vaccinia-naïve subjects will be enrolled in this trial (see [Table 4](#)). All subjects will be randomly assigned (1:1:1) to Group 1, Group 2 or Group 3. Group 1 will receive the standard regime – two vaccinations at Day 0 and Day 28. Group 2 will receive two injections at each vaccination day in the standard schedule and Group 3 will receive the standard regime and an additional early boost 12 weeks after the first dose of the standard vaccination schedule with MVA-BN® smallpox vaccine.

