### 9.1 Randomization Procedure

Randomized treatment assignments for the subjects will be done after confirmation of subject's eligibility. Subjects will be allocated randomly across the trial into Group 1, Group 2 or Group 3. Randomization will be stratified by CTS in a 1:1:1 ratio.

Please refer to trial protocol synopsis (see [Section 1.5](#)).

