## 3 Statistical Methods

### 3.1 Planned Sample Size

In addition to the below sample size calculations for the immunogenicity endpoints, a sample size of 30 per treatment group also allows for the detection of AEs with an incidence of at least 1 in 10 with a probability of detection of at least 95%.

A sample size of 30 in each group will have 80% power to detect a difference in means of 0.74 x standard deviation (SD) using a two-group t-test with a 5% two-sided significance level. This means that a difference  $\Delta$  can be detected with  $\Delta / SD > 0.74$ . Taking into account the SD of 0.85 for the  $\log_{10}$  PRNT titers the detection of a  $\log_{10}$  PRNT difference of 0.629 can be detected (or a difference in titers on the original titer scale by a factor of 4). For the ELISA where the  $\log_{10}$  SD is at most 0.42 a difference of 0.311 can be detected, i.e. a difference in titers by a factor of 2 on the original scale can be detected.

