#### 3.2.2 Per Protocol Set (PPS)

This is the subset of subjects in the FAS who have received all vaccinations, completed all visits of the active trial phase (Visit 1 to Visit 5 and additionally Visit 6 to Visit 8 for Group 3; see [Table 1](#)) and adhered to all protocol conditions. Subjects with only minor (not relevant) protocol deviations are included into this dataset.

The decision whether a protocol deviation is major or not will be made on a case-by-case basis in a data review meeting (DRM) prior to database lock.

Examples of major protocol violations are:

1. Premature discontinuation of the trial before Visit 5 for Groups 1 and 2 or Visit 8 for Group 3 (the question “prematurely terminated the trial?” is answered with “yes” even where no other reason exists to exclude the subject from further participation in accordance with the protocol)
2. Subject did not meet all of the inclusion criteria
3. Subject met one or more of the exclusion criteria
4. Withdrawal from the second and/or third vaccination

- 
5. Major vaccine preparation and administration deviation from specification as given in the protocol including cases where the subject fulfils at least one of the criteria specified in the protocol for withdrawal from vaccination
  6. Major deviations of the visit window as determined during the DRM(s)
  7. Unallowed prior or concomitant medication
  8. Missing humoral immune response data (ELISA and PRNT) at Visit 1 or 4 (or Visit 7 for Group 3)

A classification of all subjects in the FAS for major protocol deviations will be performed at the time of the DRM.

The main analysis of the immunogenicity endpoints will be performed on the PPS. The same statistical procedures will also be applied to the FAS.

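### The Group 3 versus Group 1 GMT ratios at FU 1 and FU 2 are valid but leave the pre-booster Visit 4 titre unused; a pre-specified ANCOVA beside them would usually be more precise

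*SAP*

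**What the plan says.** SAP 3.5.8 (Geometric Mean Titers) defines the durability comparison in these terms: "at the FU Visits (FU 1 and FU 2) the ratios of the GMTs will be presented between Group 3" and, separately, Groups 1 and 2. A 95% interval is stated for the Visit 4 ratio and, by the parallel wording, is meant for the others too. Neither document names a model or covariate for titres, and the sample size in SAP 3.1 also rests on an unadjusted comparison, "using a two-group t-test with a 5% two-sided significance level".

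On design, Protocol 4.1 says "Group 3 will receive the standard regime and an additional early boost 12 weeks after the first dose", so Groups 1 and 3 follow the same regimen until then. By the visit schedule, Visit 4 falls about week 6 and the booster is given at Visit 6, day 84 to 96. Under Protocol 7.1, serum is taken from all groups at Visits 1, 3, 4, FU 1 and FU 2, and at Visits 6 and 7 from Group 3 only. Visit 4 is therefore the last sample the two groups share before they diverge.

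The main immunogenicity population is the PPS. SAP 3.2.2 gives, among its examples of major violations, "Missing humoral immune response data (ELISA and PRNT) at Visit 1 or 4 (or Visit 7 for Group 3". On allocation, Protocol 9.1 states: "Randomization will be stratified by CTS in a 1:1:1 ratio".

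**The concern.** Whether the booster leaves higher antibody than the standard regimen at six and twelve months is a named secondary comparison, and Amendment 4 added FU 2 partly to obtain long-term immunogenicity data. With about 30 per group the raw ratio is imprecise.

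The Visit 4 titre measures the same analyte in the same subject, and booster assignment cannot plausibly have changed it. The trial is open-label, but the assay staff are blinded to allocation (Protocol 7.1). The plan itself pools Groups 1 and 3 at Visit 4 for the comparison with Group 2. For this one contrast, Visit 4 therefore works as a baseline.

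Randomization is stratified by site only, so nothing balances early response. The SAP will print the Group 1 to Group 3 ratio at Visits 1, 3 and 4, so an imbalance would be visible. No planned analysis takes it into account at follow-up. A chance difference at Visit 4 could then look like a booster effect, or hide one.

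**Working it through.** **Inputs.** From SAP 3.1: 30 per group, 80% power, 5% two-sided t-test, SD 0.85 (log10 PRNT) and at most 0.42 (log10 ELISA). Assumed: these SDs also hold at follow-up, and all 30 per group contribute. The correlation r between Visit 4 and follow-up log10 titres within a group is not in the documents, so a range is shown.

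**Step 1: the plan's own figure.** For a difference of 0.74 SD with 30 per group, t-test power is 80.5%. Then 0.74 × 0.85 = 0.629 log10 (4.26-fold) and 0.74 × 0.42 = 0.311 log10 (2.05-fold). The SAP figures reproduce.

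**Step 2: the planned interval.** Half-width = t(0.975; 58) × SD × √(2/30), with t = 2.002 and √(2/30) = 0.258.
- PRNT: 2.002 × 0.85 × 0.258 = 0.439 log10, so ratio ×/÷ 2.75.
- ELISA: 2.002 × 0.42 × 0.258 = 0.217 log10, so ratio ×/÷ 1.65.

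**Step 3: adjusted for Visit 4.** Half-width = t(0.975; 57) × SD × √[(1 − r²) × (2/30) × (1 + 1/56)]. The last factor is the average cost of estimating the slope.

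| r | PRNT half-width (fold) | ELISA half-width (fold) | Change from raw | Raw-analysis n per group for the same width |
|---|---|---|---|---|
| 0 | 0.443 (2.78) | 0.219 (1.66) | 0.9% wider | 29.5 |
| 0.3 | 0.423 (2.65) | 0.209 (1.62) | 4% narrower | 32 |
| 0.5 | 0.384 (2.42) | 0.190 (1.55) | 13% narrower | 39 |
| 0.7 | 0.317 (2.07) | 0.156 (1.43) | 28% narrower | 58 |

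Break-even is at r of about 0.14. Power at 0.74 SD rises from 80% to 83%, 90% and 97% at r = 0.3, 0.5 and 0.7.

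**Step 4: chance imbalance.** The standard error of the Visit 4 difference for PRNT is 0.85 × 0.258 = 0.219 log10, or 1.66-fold. Its 95% range reaches 1.96 × 0.219 = 0.430 log10, or 2.7-fold (ELISA: 0.108 log10, range to 1.6-fold). With equal SDs the carry-over into the follow-up ratio is 10^(r × imbalance). A one-standard-error PRNT imbalance therefore shifts the raw ratio by an expected 1.16-, 1.29- or 1.42-fold at r = 0.3, 0.5 or 0.7.

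**Step 5: coverage by simulation (20,000 trials).** Over all trials, coverage was about 95% with or without adjustment. Among trials with a Visit 4 imbalance above 1.8 standard errors, raw coverage was 90%, 85% and 72% at r = 0.3, 0.5 and 0.7. Adjusted coverage there stayed at about 94 to 95%.

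**Step 6: unequal correlations.** If the booster weakens the link in Group 3, the gain follows roughly the average of the two correlations. With r = 0.7 in Group 1 and 0.3 in Group 3 (average 0.5), the saving is about 13%. With 0.5 and 0.2 it is about 5%. Coverage remained 95% in both cases.

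**The case against.** The strongest reply is that nothing is wrong with the planned estimator. A raw ratio between randomised groups is unbiased, its interval already allows for chance imbalance, and it matches the t-test behind the sample size. A reader might infer that the follow-up ratio is biased or its interval invalid. Step 5 shows otherwise: the loss is of precision and of accuracy conditional on an observed imbalance. The carry-over is also partial, not one for one. This part of the reply stands.

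The stakes are also modest. The primary endpoint is safety and descriptive, and these ratios are secondary, with no margin or success rule. That stands too.

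The size of the gain is uncertain. Titres below the detection limit are set to 1, and Protocol 2.6.4 reports PRNT seroconversion of only 71 to 96% two weeks after the second dose in healthy volunteers. Some Visit 4 values may therefore sit at the floor, and the widths above assume no floor. Group 3 also receives a dose between the two measurements, over a longer gap. From the visit windows, Visit 4 to FU 1 is 166 to 198 days in Group 1 and 215 to 266 days in Group 3. A large gain should not be presumed. The risk is nevertheless lopsided: under 1% in width if r is near zero, against a material saving from about 0.4 upward.

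A reader might also take the PPS rule as a guarantee that every subject has a Visit 4 titre. It is not one. The list is headed as examples, decisions are made case by case at the data review meeting, and the mention of both assays could mean that both must be missing. Missing follow-up data are only a minor violation and titres are not imputed, so 30 per group at follow-up is optimistic. With 25 per group the raw PRNT interval becomes ×/÷ 3.04, and the saving at r = 0.5 is still about 12%.

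**Conclusion.** The point holds as one of efficiency. SAP 3.5.8 offers only an unadjusted Group 3 to Group 1 ratio at FU 1 and FU 2, although a legitimate pre-divergence covariate will have been collected and should be available for nearly all PPS subjects. Using it would probably narrow the intervals and would account for a Visit 4 imbalance. The size runs from under 1% lost (r below about 0.14) to about 4%, 13% and 28% gained at r = 0.3, 0.5 and 0.7. This rests on the design SDs at follow-up, 30 per group, no floor in the titres, and a correlation the documents do not supply.

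A reader might conclude that the adjusted estimate should replace the raw one. The documents do not support that: the endpoint is a comparison of GMTs, defined as antilogs of mean log10 titres, and the raw ratio is its direct estimate. Nor does adjustment cure everything. Group 3 PPS membership also requires the booster and Visits 6 to 8, a selection after Visit 4 that adjustment may reduce but does not remove.

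The improvement is worth making, but no success decision in the trial depends on it.

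**What to change.** In SAP 3.5.8, keep the raw Group 3 / Group 1 ratio at FU 1 and FU 2 as the endpoint-defined estimate. Beside it, pre-specify an ANCOVA of log10 follow-up titre on group and log10 Visit 4 titre, per assay and visit, fitted to Groups 1 and 3 only. Report the group difference and its 95% interval, back-transformed to a ratio.

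State that this covariate is not used for any contrast involving Group 2, whose regimen differs from Day 0 and whose Visit 4 titre is therefore already affected by treatment.

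It should be written in before database lock. The SAP's opening section requires unforeseen additional analyses to be flagged as unplanned, so an adjustment introduced after an imbalance is seen would be post hoc.

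The cost is a paragraph of SAP text and one more model per assay and visit, with no new data. Any subject without a Visit 4 titre, mainly in the FAS repeat, drops out of the adjusted estimate and appears only in the raw ratio; report the number in each.

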### 3.5.9 Adverse Events

For the treatment phase analysis a summary table will be presented of the number (and percentage) per vaccination period both per subject and for the number of events for the following events:

- Any AEs
- Any TEAEs
- ADRs (Adverse Drug Reactions)
- Treatment emergent ADRs; note that all local solicited AEs are automatically considered ADRs
- Severe TEAEs (Grade 3 or higher, for grading please refer to the CTP)
- Severe ADRs (ADR graded 3 or higher, for grading please refer to the CTP)
- SAEs
- AESIs
- AEs leading to withdrawal from vaccination
- Deaths

In addition, the incidence of AEs will be calculated (i.e. the number of subjects developing a treatment emergent AE divided by the number of subjects at the time of the vaccination) with corresponding 95% Clopper-Pearson CI. The incidence of any AE will also be calculated for each vaccination period, overall vaccination period and per subject.

For analysis of the treatment phase the information will be based on the data provided from Visit 1 to Visit 5, and additionally Visit 6 to Visit 8 for Group 3.

For the treatment phase, all AEs will be listed by subject, including demographic information, SOC and PT. Any AE with onset later than 28 days after the previous vaccination will not be included in summary tables but will be included in the listing and will be flagged accordingly as non-treatment emergent.

According to the CTP no new AEs should be reported during the FU phase, except SAEs and AESIs, but if any are reported then they will be listed but considered non-treatment emergent.

The number of subjects with at least one treatment emergent AE during the treatment phase will be descriptively compared between the treatment groups, and between vaccination periods within Group 3.

#### Serious Adverse Events

The number of subjects with at least one SAE during the trial will be descriptively compared between the treatment groups, and between vaccination periods within Group 3.

SAEs reported will be listed in the same manner as for AEs.

The number of subjects with at least one Treatment Emergent SAEs will be descriptively compared between the treatment groups, and between vaccination periods within Group 3.

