The targeted population will be HIV-infected subjects with a current CD4 count between 100 and 500 cells/ $\mu$ l combined with a nadir CD4 cell count category 3 (documented CD4 count < 200 cells/ $\mu$ l at any time prior to enrollment). To account for the expected impact on the immune response to vaccination in this population, the trial will evaluate whether increasing the number of doses can improve the immune response to MVA-BN® compared to the standard dose regimen in highly immunocompromised individuals, while still being comparably safe and well tolerated. MVA-BN® will be administered either by simultaneous administration of two standard doses to achieve a higher total dose, or in a three dose schedule by adding a third standard dose as early booster 12 weeks after the first vaccination. Durability of immune response in this population will be evaluated at the six months FU visit - which is comparable to the accepted follow-up period in already completed clinical trials in healthy and HIV populations vaccinated with MVA-BN® smallpox vaccine.

This trial will generate important additional data in a highly immunocompromised population.

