#### **5.1 Recruitment Procedure**

Subjects will be recruited actively. Recruitment strategies, including IRB approved advertisements, will be evaluated by the Sponsor.

30 subjects will be enrolled in each group (90 in total).

---

After signing the ICF and HIPAA, subjects undergo screening procedures to check eligibility according to the inclusion/exclusion criteria. In the event of a screening failure secondary due to mild or limited acute illness or abnormal laboratory values, the subject may be re-screened after resolution of the event. Re-screening may require only an additional blood draw or a complete re-screening evaluation, depending on the circumstances of and the time interval from the initial screening failure (see also [Section 4.2.1](#)).

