**Figure 3 Algorithm for Reporting of AESIs**

## 9 Statistical Considerations

The primary endpoint of this trial is to compare the occurrence, relationship and intensity of any serious and / or unexpected Adverse Event at any time during the trial. This analysis will be descriptive.

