## **1 Trial Overview**

### **1.1 Trial Description**

This trial is a randomized, open-label Phase II trial to assess the safety and immunogenicity of MVA-BN smallpox vaccine when increasing the number of injections compared to the standard regimen in immunocompromised subjects with HIV infection.

In total, ninety (90) vaccinia-naïve Human Immunodeficiency Virus (HIV) infected subjects will be enrolled in this trial. All subjects will be randomly assigned (1:1:1) to one of three groups (Groups 1-3) to receive:

Group 1:

One injection at Day 0 and Day 28 with 0.5 mL Modified Vaccinia Ankara Strain – Bavarian Nordic (MVA-BN) smallpox vaccine containing at least  $1 \times 10^8$  Tissue Culture Infectious Dose 50% (TCID50) per mL (standard regimen)

Group 2:

Two injections at Day 0 and two injections at Day 28 with 0.5 mL MVA-BN smallpox vaccine each containing at least  $1 \times 10^8$  TCID50 per mL (double dose regimen)

Group 3:

One injection at Day 0 and Day 28 with 0.5 mL MVA-BN smallpox vaccine containing at least  $1 \times 10^8$  TCID50 per mL (standard regimen) and one booster injection at Day 84 (Week 12) with 0.5 mL MVA-BN smallpox vaccine containing at least  $1 \times 10^8$  TCID50 per mL (booster regimen)

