### **1.2 Objectives**

#### **1.2.1 Primary Objective**

To assess the safety of MVA-BN smallpox vaccine when increasing the dose or number of injections compared to the standard 2-dose regimen.

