### Seroconversion rates

Vaccinia-specific seroconversion rates measured by ELISA and PRNT will be presented by treatment group for Visits 3, 4, 6, 7, FU 1 and FU 2 (and for combined groups as indicated) along with the Clopper-Pearson 95% CIs of the seroconversion rates.

In addition, the difference in seroconversion rates of Group 2 at Visit 4 will be compared to the combined Group 1 / Group 3 seroconversion rates and will be calculated as

Difference in seroconversion rates =

$$\{ \text{Group 2 seroconversion rate} \} - \{ \text{combined Group 1 and Group 3 seroconversion rate} \}$$

along with an exact 95% CI calculated following the “Invert two one-sided tests” method of Chan and Zhang ([Chan, 1999](#)).

Similarly, the difference between the seroconversion rate at Visit 7 for Group 3 and the seroconversion rates at Visit 4 for Group 1 and Group 2 (separately) will also be calculated along with the exact 95% confidence interval.

For both the FU Visits (FU 1 and FU 2) the difference of the seroconversion rate for Group 3 will be compared to the seroconversion rate of Group 1 and Group 2 separately.

Lastly, the difference of the seroconversion rates for Group 1 will be compared to the seroconversion rates of Group 2 and Group 3 separately at Visit 3, Visit 4, FU 1 and FU 2.

A bar chart will be presented showing the seroconversion rates measured by ELISA and PRNT per treatment group for each visit for the PPS and the FAS.

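### The primary objective is safety relative to the standard regimen, but no safety endpoint gets a between-group estimate or interval; adding descriptive risk differences would be a cheap improvement

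*SAP*

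**What the plan says.** The primary objective (SAP 1.2.1) is "To assess the safety of MVA-BN smallpox vaccine when increasing the dose or number of injections compared to the standard 2-dose regimen". Protocol section 9 describes the primary endpoint as a comparison of serious or unexpected adverse events (AEs), and adds: "This analysis will be descriptive". Protocol 2.7 gives the background aim: to see whether more doses improve the immune response "while still being comparably safe and well tolerated".

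The planned safety analyses are these:
- **SAP 3.5.3 (primary endpoint):** a listing of SAEs and a listing of AESIs.
- **SAP 3.5.9, SAEs:** "The number of subjects with at least one SAE during the trial will be descriptively compared between the treatment groups". AESIs are reported the same way, and subjects with treatment-emergent AEs are also compared descriptively.
- **SAP 3.5.9, AE incidence and solicited AEs:** Clopper-Pearson 95% intervals within each group.
- **SAP 3.5.1:** a general rule that categorical tables show counts, percentages and a confidence interval unless stated otherwise, split by group.

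For seroconversion, SAP 3.5.8 gives group differences "along with an exact 95% CI calculated following the" two one-sided tests method of Chan and Zhang. It also presents ratios of geometric mean titers (GMTs) between groups. The table index in SAP 5.1 has 16 comparison tables for seroconversion and GMTs, and none for safety.

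**The concern.** The objective asks how the two intensified regimens differ from the standard one. The planned output describes each group separately and leaves the reader to form the difference. A one-group interval does not state what excess over Group 1 the data still allow. With few events in 30 subjects per group, that excess is large, and no figure in the plan shows how large. What is at stake is how precisely the primary question is answered. The validity of the data is not in doubt.

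**Working it through.** **Inputs from the documents.** 30 subjects per group, allocated 1:1:1 (Protocol 5.1, SAP 1.1). The only safety sizing statement is in SAP 3.1: an "incidence of at least 1 in 10 with a probability of detection of at least 95" per cent. No safety hypothesis, margin, expected SAE rate or dropout allowance is given.

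**The plan's own figure.** P(at least one event in 30 | rate 0.10) = 1 - 0.9^30 = 0.958. The stated figure of at least 95% reproduces. It concerns one group and says nothing about a difference.

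**What the one-group interval shows.** For 0/30 the two-sided 95% Clopper-Pearson upper limit is 1 - 0.025^(1/30) = 11.6%. For 1/30, 2/30 and 3/30 the upper limits are 17.2%, 22.1% and 26.5%. Zero events in 30 is unremarkable at low true rates: 0.99^30 = 0.74, 0.98^30 = 0.55, 0.95^30 = 0.21.

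**What the difference interval shows.** The method is the one named in SAP 3.5.8. For each candidate difference d, compute the score statistic with rates restricted to differ by d. Take each one-sided exact p-value at its maximum over the unknown common rate, and keep every d with p > 0.025. With 30 per group, on a 0.25-point grid:

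| Events, new v standard | Difference (points) | Exact 95% CI (points) |
|---|---|---|
| 0 v 0 | 0 | -11.75 to +11.75 |
| 1 v 0 | +3.3 | -8.5 to +17 |
| 2 v 0 | +6.7 | -5.25 to +22 |
| 3 v 0 | +10 | -2.25 to +26.5 |
| 1 v 1 | 0 | -14 to +14 |
| 2 v 1 | +3.3 | -11 to +20 |

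Newcombe intervals agree closely: ±11.4 for 0 v 0, and -10.8 to +18.2 for 2 v 1.

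**Where the difference adds most.** When Group 1 has no events, the upper limit of the difference almost equals the one-group upper limit (11.75 v 11.6, 17 v 17.2, 22 v 22.1, 26.5 v 26.5). The gain comes when both groups have events, as with solicited reactions. Assume, for illustration, 50% of subjects in each group with a solicited local AE. The large-sample 95% half-width is 1.96 × √(0.25/30) = 17.9 points for one group, and 1.96 × √(2 × 0.25/30) = 25.3 points for the difference. Two one-group intervals do not display the second figure.

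**Observation windows.** Groups 1 and 2 share one schedule. Group 3 has a third vaccination period, AE recording to Week 16 rather than Week 8 (Protocol 8.1.2.1), and the one-year follow-up visit (FU 2) at target Week 64 rather than 56 (Protocol 1.6). A raw per-subject difference between Groups 3 and 1 therefore mixes regimen with observation time. The planned comparison of counts has the same problem.

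**The case against.** The strongest reply is that this is a disclosed design choice. The protocol says the primary analysis is descriptive, sets no margin, and sizes safety within a group. The two-group calculation in SAP 3.1 belongs to titers, so treating safety and immunogenicity differently is not in itself an inconsistency. The endpoint as defined in SAP 1.4.1 is occurrence, relationship and intensity, which is not comparative wording. The plan also offers more than bare counts: percentages per subject and per vaccination period, incidence tables for SAEs and AESIs, and one-group exact intervals. If the general rule in SAP 3.5.1 is applied to SAEs, the 11.6% limit for 0/30 already shows the limitation in the zero-event case. All of this stands, and it is why the point is an improvement and not a fault.

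It does not remove the gap. A difference with an interval is itself descriptive, and the SAP already presents seroconversion that way with no test.

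A reader might infer more: that the sponsor plans to conclude comparable safety from sparse counts, or that safety has no intervals at all. The documents support neither. The wording on comparable safety stands in the rationale and is not a decision rule or a planned conclusion, and one-group intervals are planned. Nor does the width of the intervals show that the trial is too small for its stated purpose, because no safety difference was ever to be tested.

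**Conclusion.** The point holds as a cheap improvement to a descriptive analysis. The primary objective is relative to the standard regimen, yet no safety endpoint has a planned between-group estimate or interval, while a secondary immunogenicity endpoint does. At 30 per group, 0 v 0 subjects with an SAE leaves about ±12 points compatible with the data, and 2 v 0 leaves about -5 to +22. These sizes assume all 30 subjects per group are evaluable, and the event counts are illustrative. The width follows from the sample size. Reporting the difference makes it visible but does not reduce it.

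**What to change.** In SAP 3.5.3 and 3.5.9, add descriptive risk differences, Group 2 minus Group 1 and Group 3 minus Group 1, each with the exact 95% interval already named in 3.5.8. Do this for subjects with at least one:
- SAE;
- AESI, counting serious AESIs, which the SAP's General Definitions otherwise move out of the AESI analysis;
- related AE of Grade 3 or higher;
- solicited local AE;
- solicited general AE.

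For Group 3 minus Group 1, state the window. The main contrast can cover vaccination periods 1 and 2, or be made per vaccination. Groups 1 and 3 receive the same vaccinations through period 2, so only the per-vaccination form, such as Group 3's third period against a Group 1 period, can bear on the booster. Show the whole-trial contrast alongside, labelled as including the extra vaccination period and the longer follow-up.

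In the study report, state which excess over Group 1 the intervals exclude and which they do not. Do not declare comparability, since no margin is set.

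The cost is some programming with a method already in the plan: five endpoints × two contrasts = ten intervals, plus the second window for Group 3. No subjects, data, test or alpha are added. The downsides are several unadjusted intervals that must be read as descriptive, and a more cautious safety statement. The list does not cover the unexpected-event part of the primary endpoint, for which SAP 3.5.3 and 3.5.9 define no count.
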